Exit Interviews. To provide insight into why CHALO! may or may not have worked to increase HIV testing and linkage-to-care for HIV+ and for HIV- individuals, and get additional insight to inform intervention strengthening and scale-up, research staff at HST will perform brief phone-based exit-interviews with 5 to 10 randomly selected participants from each of the following groups: never HIV-tested, HIV-tested only once, HIV-tested multiple times, linked to HIV treatment (if positive), linked to prevention care (e.g., PrEP, safer-sex counseling), and those not linked to care. In addition, the research team at HST will attempt to interview all participants who test positive to explore potential missed opportunities for prevention to inform future efforts. Data will be audio-recorded, but kept anonymous and not linked to any other data source. Interviews will be performed by the India Co-Investigators.

A3. Potential Risk to subjects

We believe that the risks posed to participation in our study are minimal and no greater than what individuals encounter in their regular use of the Internet and SMT services. The primary risks of this study are: (1) breach of confidentiality leading to embarrassment or “outing” of an individual’s sexual orientation, (2) breach of confidentiality leading to disclosure of an individual’s participation in a HIV prevention intervention, (3) inconvenience and discomfort associated answering questions about sexual health behavior, (4) stigma and confidentiality concerns when engaging in HIV testing

Confidentiality issues: The research team at HST will collect limited personal information from participants to facilitate follow-up and will be asking personal questions about substance use, HIV risk behaviors, and sexual identity. We have outlined procedures to address maintaining confidentiality below (see section B3a).

Inconvenience and discomfort associated with interviews: In all surveys, participants will be asked about HIV risk behaviors, sexual activity, and/or substance use. It is possible that such questions could produce anxiety in participants. Participants will be instructed that they may refuse to answer any question without providing justification and/or may withdraw from the study if this occurs.

Stigma and Confidentiality Concerns in Terms of HIV testing: Individuals make decisions about where and how to get HIV-tested by weighing multiple perceived and actual risks/benefits of each testing strategy in the real-world, such that no single testing approach likely meets the need of majority of MSM. CHALO! 2.0 uses a pragmatic approach by linking individuals to multiple exiting testing options. The coupon will be linked to participants’ mobile numbers, and will be scanned/entered into an online system by testing staff (at HST or the private laboratory), at which time participants will immediately receive a code to provide to the tester to verify eligibility as a study participant. This will discourage sharing and use of the coupon aside from the participant, and help protect the participant’s privacy. Each coupon can only be used

once every four-weeks at the most to minimize increased harm from potential false positive due to frequent testing and to discourage sharing the coupon. All participants who get tested, will also receive an automated message with a link for a pre- and post-test counseling video, a brief, bulleted Whatsapp message covering the central points of the counseling videos, and contact information for HST's community health-worker (who can provide counseling and linkage-to-care/navigation services for both prevention and treatment, and will be blinded to participant's study condition). These steps will help ensure confidentiality of participant test results, linkage of valid test results to each participant, and ensure data integrity.

Being Outed as a sexual minority. Participation in the study could theoretically out someone if another individual saw contents on the participants Whatsapp messages about MSM health and HIV testing. However, participation in this trial is voluntary, and is not likely to pose any greater risk than already experienced by potential participants who are using gay/MSM dating apps on their mobile phones, may be having text message conversations with other gay/MSM, or accessing LGBTQ related contents from their phones. Participants will only be receiving twice weekly messages/contents – which will only be sent during daytime hours. Additionally, participants will only be contacted by online peer-counselors or healthcare workers by the method the participant indicated during enrollment.

B. ADEQUACY OF PROTECTION AGAINST RISKS.

B1. REGULATORY COMPLIANCE.

We will follow procedures as outlined by the National Institute of Mental Health (NIMH) Internet-based Research Interventions: Suggestions for Minimizing Risk (2007) and other evolving best practices in ethical conduct of social media and Internet research.^{35,63,101-103} Additionally, the research team at HST will work with our social media consultants to ensure technical capacity of maintaining ongoing security and privacy.

B2. RECRUITMENT AND INFORMED CONSENT.

Members from the research staff at HST will first be conducting a quick screener that will not require potential participant to enter any identifiable information. Then, online informed consent will be obtained from eligible participants prior to providing the baseline self-administered online questionnaires and collection of any automated process data. Online informed consents will be provided in two ways: (1) A recorded video of the informed consent text and (2) the same information will be provided in an easy to read text format. A link for emailing or direct messaging and contact information with the PI and Research Assistant's office phone numbers will be displayed for potential participants to ask any questions participants might have. To indicate consent, an individual will then click a box attesting to their consent and then clicking a "submit" button. After consenting, participants will be taken directly to an eligibility screener which will continue seamlessly to the baseline survey (for eligible participants) or to an exit page thanking them for their interest. As part of the baseline survey and enrollment, potential participants will need to provide a phone number associated with their WhatsApp account and an email, and reply to confirmation code (sent immediately) to verify their information, subsequently receive their incentive, and be considered fully enrolled.

B3. PROTECTIONS AGAINST RISK.

B3a. Protection of confidentiality Questions pertaining to substance abuse, sexual activity and identities requires special sensitivity to issues of confidentiality. Participant confidentiality will be carefully protected. The researcher staff at HST will institute the following processes to ensure confidentiality is maintained:

1. Research staff at HST will be using Avegen Health Machine (HM) for data collection – this system uses Transport Layer Security (TLS) encryption (also known as HTTPS) for all transmitted data. Avegen HM hosts all data in in trusted data centers that are independently audited using the industry standard SSAE-16 method. Avegen HM deploys the general requirements set forth by many Federal Acts, including the FISMA Act of 2002, and they meet or exceed the minimum requirements as outlined in FIPS Publication 200. Avegen HM also institutes HITECH (Health Information Technology for Economic and Clinical Health Act) updated HIPAA rules to ensure that data are properly protected and best security practices followed and safeguards all customer data, and uses secure data centers to ensure the highest protection as per HITECH requirements. Additionally, Avegen HM allows us to assign individuals different levels of access to the system and data and allows monitoring of data access and flags/rules can be created for any potential suspicious activity (e.g. a user accessing the system outside expected working hours). The full dataset will only be accessible to the PI and study staff that need all such data (which will be rare).
2. Whatsapp will be the primary platform for intervention delivery and communication with participants. WhatsApp's uses an end-to-end encryption, which ensures only the study team and the participant with can read what is sent, and nobody in between, not even WhatsApp. This is because the messages are secured with a lock, and only the recipient and the sender have the special key needed to unlock and read them. For added

protection, every message sent on Whatsapp has its own unique lock and key, and all of this happens automatically. Thus, this messaging approach is the most secure way to deliver intervention contents and balance using a user-friendly platform that ensures engagement.

3. The research team will also consult with our social media technology consultants to provide ongoing advice on technical aspects of securing information over the Internet and social media and in particular Whatsapp, Avegen HM, and protecting participant data.
4. An electronic, password protected and encrypted system will be used to store analyses, and Whatsapp activity will remain private to study participants.¹⁶⁴ Research participants will be informed of how communications are recorded and stored during the online informed consent process. Due to the ever-changing and evolving nature of privacy issues on messaging platforms, smartphones, the Internet, the research team and our technology consultant will regularly review privacy settings for all online platforms used in the study at least every month and adjustments will be made to protocols if necessary to ensure security.
5. Data analyses and reporting will be conducted using de-identified data in so that no participants will be identifiable. In order to deliver electronic gift card incentives, participants will be asked to provide their mobile number and an e-mail address where we can send incentives (requirement for enrollment). However, researchers at HST will not request names (regardless, there is no way to ensure we are getting actual or alias names and so there is little utility in collection of information). All participant responses will be kept confidential. Only appropriate research staff, and *not* the Peers will be able to review raw survey responses and un-summarized web activity. At all times, data collected for the project will be downloaded onto secure servers and stored in password protected encrypted files.
6. All research having any potentially identifying information such as this proposal, will have a Certificate of Confidentiality automatically issued by NIH, as data will be stored on secure servers at Albert Einstein College of Medicine.

B3b. Data Security and

B3d. Managing the matter of anonymity and/or false information of research participant/study: The research team at HST will conduct meetings with all supporting research staff to discuss site activity, messaging, and participant responses to scan content for false information. Email and mobile phone numbers will be verified by sending an email and Whatsapp message to each potential research participants and requiring a verification response via clicking a link in the email and responding to the Whatsapp message. To protect false information, participants will provide basic demographic information again when participating in the assessment surveys, and online gift-card incentives that will be provided for completing surveys can only be sent to the mobile number once each data collection wave.

B3e. Protecting participants from research “posers”: Research participants will be provided with options for verifying the credentials of the researchers and approval of the study through provided contact information of the site PI, research assistant, and the local IRB(for international site) and approval number (phone number, email, institutional website); a signed certificate and SSL (Secure Sockets Layer) for all data transfer over the Internet will be used, provided by our technology partner; participants will be given the option to print or save the informed consent page for their personal records and receive it via email from the study team.

B3f. Monitoring the research participant’s well-being and building trust: If a participant reveals symptoms of psychological distress via SMT interaction with the online-peer counselors, appropriate referrals and follow-up care and intervention will be made by the HST health workers and online peer-counseling staff in accordance with existing protocols for online/phone counseling by HST outreach workers and with a developed resource guide. All efforts will be made to link the online participant to resources at the HST health resources or to one of HST’s vetted partners.

B3g. Addressing the lack of in-person communication and possible needs of research participants: Graphics and video will be used for participants to help overcome limited literacy. Additionally, all participants, regardless of arm, will be able to communicate via SMT with online peer-counselors at HST. Participants will be able to directly contact the research team (site PI, PI, and Project Director) through email and phone, and this information will be readily accessible in the customized Website link.

B3h. Managing confusion among research participants and debriefing: Research participants will have the opportunity to leave comments and ask questions about the online assessments/surveys both before and after completion, and additional contact information of the research team will be made readily available to all participants.

B3. Data Security for Storage and Transmission: As outlined above, all data collected online will be maintained in encrypted, password protected computer systems. Study data will be stored in the web-based Avegen Health Machine (HM) software database to hold study data – this system uses the latest encryption data and in the U.S. meets all regulations for security and privacy of participant information. Avegen HM will be used to collect web-based survey responses – which also uses the latest security protocols for transmission and receiving online data. All data can only be accessed by logging into the online Avegen HM database and different study staff can be given different levels of access as required – all of which facilitates security, privacy. This system is used by Research centers across the world including in India (e.g., AIDS Society of India for a study with HIV positive individuals, Prashanti Cancer Center in Pune, KLE JN Medical College, etc.). All offline data, if it exists, (which we expect there to be minimal to none) will be stored in the cupboards at HST under lock and key. All data will be deidentified prior to any analysis and reports. Only members of the research team who are in charge of follow-up and the investigators will have access to the data of participants who agree to be a part of the follow-up. Their identifying information will be destroyed at the conclusion of the project.

B4. Additional Online Safety and Suicidal ideation protocol

The following protocol has been approved by our IRB and is being used in our current social media/online research studies²¹². Given that we cannot actually verify real-world identities of participants and will not be collecting residential address/location information (to encourage participation and help minimize perceived breaches of privacy), the following protocol will allow us to monitor and address safety concerns of participants in a timely manner to the extent possible. While our study poses no more than minimal risks already being encountered by potential participants, these measures and protocols will be in place to maintain adequate protection of participants in the event they are needed.

1. If online peer counselors' sees a status update display on study sites or receives email, phone calls that suggests suicidal ideation. Key words for example may include (but are not limited to) "kill myself," "end it all," "not be around anymore," "better off dead" or themes alluding to these issues, including any description of an intended activity linked to suicide such as "I'm going to jump off a bridge," "I'm going to shoot myself," they will follow standard operating procedures at HST for such occurrences as HST deals with these issues regularly.

Additionally, because subjects are volunteering for a research study, the HST research team will employ the following procedures:

- a. Peer-counselors notes date and time of reference
 - i. Write down name and any available contact information for that profile owner on a document separate from the data collection sheet for this study.
 1. If reference is within the last 72 hours, calls Project Manager (TBD) and [name] (Site PI) immediately. If for some reason they are not reachable by cell phone, or email within 4 hours, call the IRB.
 2. If reference is older than 7 days but no status updates since, call [name] (Site PI) immediately.
 3. If reference is older than 7 days, read status updates since and note any references to "feeling better" or similar comments. If these are present, discuss with [name] the next day during business hours.
 4. Peer-counselor will contact participant immediately upon noticing the information and provide telephonic counseling and will attempt to refer them to in-person services, per current HST protocols.

2. Protocol for acute SI noted on profiles (within last 7 days)

- a. Online peer-counselors will reach out to the individual by phone and then text messages and follow standard operating protocols for such situations that they currently employ.
- b. Additionally, Online peer-counselors will notify [name] (site PI) and the Project Manager immediately.
- c. [name] and the Project Manager will perform status check on the individual participant. The Site-PI and Project Manager will debrief with online peer-counselor and assess adequacy of response. If acute SI issue is resolved with a safe-plan, this will be documented and submitted to the IRB.
- d. For participants who do not have a resolution, participant will be called using the WhatsApp phone number they enrolled in the trial, emailed, and contacted with any other information they may have provided. If participant is not reachable within one hour, a member from HST's research team will call any emergency contact they may have provided. This protocol will be made known to participants during the informed consent.

- e. As per existing protocol and training at HST, online peer counselors will continue reaching out to the participant regularly as deemed necessary and linked to appropriate resources (i.e., professional counselor at HST or outside clinic).

C. POTENTIAL BENEFITS OF THE PROPOSED RESEARCH TO HUMAN SUBJECTS AND OTHERS

The potential benefit to participants in this study could be linkage-to-care, access to HIV/STI prevention and testing services otherwise difficult to obtain, and access to credible information on new and existing HIV prevention tools. But all participants may not realize these benefits and there will be no other direct benefits to participants. However, if effective, CHALO! 2.0 could be implemented broadly and rapidly diffuse information on available HIV prevention tools and improve linkage to HIV testing and linkage to care services for MSM, a hard-to-reach population. Additionally, CHALO! 2.0 could have significant public health benefit by reducing the HIV burden in MSM and the broader population.

Potential Benefits to control condition participants: Participants in attention matched control condition will receive non-overlapping health information about general health topics as prioritized by MSM in Mumbai themselves based on a recent study by our team. This will include topics on physical fitness, diabetes, heart disease, and nutrition during the 12-week intervention period and a free HIV testing coupon. Both the attention matched control and the digital coupon only conditions will both receive digital coupons for free HIV testing to 41 private lab sites and 3 MSM community based testing locations throughout Mumbai, and a link to a Website with information about different HIV testing sites. The digital coupon addresses important structural barriers to testing. Thus, in this pragmatic study, all conditions are receiving some level of outreach, beyond what is currently available or standard of care. At the end of the follow-up period, after the final participant completes the final assessment survey, participants will be given access to all CHALO! 2.0 components if they choose to receive this information.

C1. Risk/benefit ratio. CHALO! 2.0 has the potential to increase reach of HIV prevention programs and services, increasing HIV Testing and linkage to care, and serostatus awareness. If effective, CHALO! 2.0 could be broadly implemented by health centers and community-based organizations, and reduce HIV transmission and promote healthy behaviors. Additionally, this level of outreach may foster social support and self-efficacy. Given the steps that the research team will take to minimize the chances of breach of confidentiality, participating in this study presents low risk and the risk/benefit ratio is favorable.

D. IMPORTANCE OF THE KNOWLEDGE TO BE GAINED

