Sociodemographic characteristics	Zero Meters Away ²³	●				
Sexual behaviors, partners, condom, PrEP, and PEP use	Zero Meters Away ^{23,42}	●	●	●	●	●

8.1 Online study assessments: The researchers at the international site at HST will use Avegen HM online surveys to collect self-reported data on sexual behaviors, prior HIV testing, HIV knowledge (transmission, treatment, and prevention), self-efficacy for HIV-testing and care, stigma, and other covariates listed in Table 2. The survey will be in Hindi and English, and will also ask questions to assess potential contamination between study arms. At each assessment point, subjects will receive 3 automated reminders, 48 hours apart if surveys are not completed. After the 3 automated attempts, study staff will be notified if surveys are not completed, who will then reach out to participants.

8.2 HIV testing digital coupon data:

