- Secondary outcomes: HIV treatment linkage (yes/no) and ART initiation (yes/no) for those testing HIV positive, each variable individually in the primary composite outcome (i.e. counseling, PrEP), sexual behavior (consistent condom use, number of partners).
- Exploratory Outcomes: include alcohol/substance use, PEP use, STI testing/treatment, and type of prevention or treatment care site accessed (i.e. HST vs. other).

Finally, the following outcomes will be reported by study arm: HIV knowledge, HIV- and MSM-stigma, risk-perception, self-efficacy, social support, intention to obtain HIV test in next one month, and SMT engagement by arm (proportion of all messages viewed, website visit, and any communication with online-peer counselors).

11. Plans to identify contamination across study arms. Contamination will be assessed by using a content recall questionnaire^{86,87} to measure any diffusion and sharing of **CHALO! 2.0** and attention matched control contents, determining whether participants report sharing messages or website links. Participants will also be asked if they knew anyone participating in the study and if they received any contents from them.⁹⁵ Members from the HST and Einstein research teams will assist in building research instruments.

12. Randomization checks and missing data. A member from either the Einstein or HST team will first review and summarize data using descriptive summaries and graphical analyses to ensure that reported values are within appropriate ranges, check for outliers and abnormal values, and verify that distributions of measures meet

assumptions of planned statistical tests. The Einstein and HST research teams will also explore whether **CHALO! 2.0** and the 2 control groups are equivalent on potential confounders (e.g., sexual identity, income, age, education, intention to test, and sexual behaviors. If these variables differ between groups, we will include them as covariates in multivariable analyses (see Section C.7.4). For missing categorical data, we will use multivariate multiple imputation using the fully conditional specification method.⁹⁶ We will repeat imputations 5 times, and then compare statistical results using datasets that include imputed values and the dataset that drops missing values. This will guide interpretation of our assessment of the impact of missing data on our study findings, as well as our interpretation of overall results.

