Power	CHALO! 2.0 ($n_1=300$)	attention-matched control ($n_2=300$)	Digital coupon only ($n_2=300$)
>99%	0.5-0.75	0.2-0.5	0.15-0.45
>93%	0.5-0.6	0.35-0.45	0.35-0.45
>59%	0.5-0.6	0.4-0.5	0.4
>15%	0.5	0.45	0.45

*power is for CHALO! compared to each control separately

report HIV- testing, or condition,

13.2 Aim 1 sample size considerations: With a total of 1,000 participants, we expect at least 900 participants at 6 months, and 800 participants at 12 months. This will provide a total of 300 participants per arm at 6 months, and 266 participants per arm at 12 months. Based on findings from online intervention studies of HIV testing showing 1.7-2.2 increases in odds of testing in intervention vs. control conditions (across low and high income countries and heterogeneous online interventions),⁹⁷⁻¹⁰⁰ we estimate the proportion HIV testing at 6 months to be 70% for **CHALO! 2.0** ($n_1=300$) vs. 35% for attention-matched control ($n_2=300$) and 30% for digital coupon only ($n_2=300$). With the expected sample, the study's 2 main effects (**CHALO! 2.0** vs. attention-matched control and **CHALO! 2.0** vs. digital coupon only) have >99% power (Table 3). We also provide power estimates based on a wider range of parameters in Table 3, showing that we have sufficient power to detect between-group differences in the primary outcome with smaller effect sizes. Power was calculated using PASS software V15.0, with all analyses conducted with a two-tailed alpha of .025, resulting in a family-wise error rate of at most 0.05 for the primary outcome.

13.3 Aim 2 analyses: To test the hypothesis that **CHALO! 2.0** participants will be more likely to be linked to care (vs. controls), we will compare rates of linkage-to-prevention (i.e. counseling, PrEP-initiation) at 12 months among HIV-uninfected participants between study arms. As for Aim 1, we will perform 2-sample comparisons of proportions using chi-square tests, and will also perform logistic regression with linkage-to-prevention by 12 months as the outcome and study arm as the primary predictor, adjusting for covariates in Table 2 as required. We will repeat these analyses with linkage-to-care outcomes at 18 months, and with the outcome of self-reported linkage-to-prevention by 18 months. Additionally, using the entire study cohort, we will

Table 4. Proportion linked to HIV prevention by 12 months

Power	CHALO! 2.0 ($n_1=247$)	attention-matched control ($n_2=139$)	digital coupon only ($n_2=108$)

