>99%	0.15-0.4	0.05-0.1	0.03-0.01
>98%	0.3-0.4	0.1-0.2	0.03-0.01
>90%	0.3	0.15	0.1-0.15
>70%	0.2	0.1	0.08
>49%	0.3	0.2	0.2
>21%	0.15	0.1	0.1

*power is for CHALO! compared to each control separately

months, explore

whether participant factors and testing strategy predict HIV prevention (counseling or PrEP use) and treatment (ART initiation). For secondary and exploratory outcomes (defined in C7.1), we will repeat analyses as above, using ANOVA for or chi-square tests as appropriate.

13.4 Aim 2 sample size considerations: We anticipate that there will be no higher than 7% prevalence of undiagnosed HIV. Combined with expected HIV testing rates by 12 months of at least 75%, 45%, and 35% in the three arms, we anticipate the available sample size of HIV-uninfected participants for Aim 2 to be **CHALO! 2.0** ($n_1=247$), attention-matched control ($n_2=139$), and digital coupon ($n_2=108$). Based on HST's current linkage-to-care rates for HIV- negative individuals (30%),⁹⁰ we expect the rate of linkage-to-prevention care at 12 months to be 30% for **CHALO!** vs. 15% for attention-matched control vs. 5% for digital coupon only. The study's 2 main effects (**CHALO!** vs. Attention-matched control and **CHALO! 2.0** vs. digital coupon only) have >90% and >99% power, respectively (Table 4). We also provide power estimates for smaller effect sizes. The power was calculated using PASS software V15.0., with a two-tailed alpha of .025, resulting in a family-wise error rate of at most 0.05 for the primary outcome in the Aim 2. Due to an expected overall small number of individuals testing HIV- positive, we will not have power to detect potential differences between arms.

PROTECTION OF HUMAN SUBJECTS

A. RISKS TO HUMAN SUBJECTS

A1. HUMAN SUBJECTS INVOLVEMENT, CHARACTERISTICS, AND DESIGN.

A1a. Proposed human subject involvement. The protocol will include a 3-arm parallel, single blind, pragmatic randomized control trial of an online HIV digital messaging intervention (CHALO! 2.0) compared to an Attention-Matched Control, or a Digital Coupon only. Through online surveys, HIV testing utilization and results, and clinic visit data tracked by HST healthcare workers during the 12-week intervention period, and during the 15 months of follow-up, we will evaluate the outcomes for CHALO! 2.0.

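### For number of partners and condom use, the plan guarantees neither adjustment for the outcome's own baseline and the randomisation stratum nor the two CHALO! 2.0 versus control contrasts

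*Combined protocol and SAP*

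**What the plan says.** All references are to the combined protocol and SAP.

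- **Outcomes.** Section 10 lists among the Aim 2 secondary outcomes "sexual behavior (consistent condom use, number of partners").
- **Measurement.** Table 2 has a covariate row "Sexual behaviors, partners, condom, PrEP, and PEP use", marked at months 0, 3, 6, 12 and 18.
- **Tests.** For secondary and exploratory outcomes, Section 13.3 says "we will repeat analyses as above, using ANOVA for or chi-square tests as appropriate". In the text available to us, the words after ANOVA that would name its target are missing. That may come from the PDF reading and is not counted against the plan.
- **What the sentence points back to.** Earlier in Section 13.3: "As for Aim 1, we will perform 2-sample comparisons of proportions using chi-square tests", together with logistic regression "adjusting for covariates in Table 2 as required".
- **Imbalance rule.** Section 12 compares the arms on a list of possible confounders that includes sexual behaviours. It adds: "If these variables differ between groups, we will include them as covariates in multivariable analyses".
- **Contrasts.** The footnote to the power tables reads "power is for CHALO! compared to each control separately", and Sections 13.2 and 13.4 name the same two main effects.
- **Stratification.** Section 7 stratifies randomisation by prior HIV testing history.
- **Other count outcome.** Section 13.1 gives number of HIV tests a Poisson test and a Poisson regression.

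**The concern.** A participant's baseline level of a behaviour usually predicts the later level of the same behaviour. Having it in the model buys precision at no cost, because the data are already being collected. The plan allows this but does not require it.

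A rule that adjusts only when the arms differ misses the main benefit. The precision gained from a prognostic covariate does not depend on chance imbalance, and such a rule leaves the model to be chosen after the data have been seen. The stratification factor is in a weaker position still. It is balanced by design, so an imbalance rule would hardly ever select it. It is not in Section 12's list of examples, and the covariate rows of Table 2 have no row for prior testing history.

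The second issue is the contrast. The trial asks two questions, CHALO! 2.0 against each control. If ANOVA were applied across all three arms, its F test would also respond to a difference between the two controls, which is no stated hypothesis. What is at stake is the precision and interpretability of secondary results.

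**Working it through.** The plan gives no power, mean, standard deviation (SD), dispersion or baseline correlation for these outcomes, so there is no stated figure to reproduce.

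**Inputs.** 266 per arm is the plan's 12-month figure (Section 13.2). The two-sided alpha of 0.025 per contrast is the plan's own (Section 13.2), although family-wise control is claimed only for the primary outcomes. The correlation rho between baseline and follow-up is assumed, 0.3 to 0.6. The plan names no time point for these outcomes, so 266 is itself an assumption. If the analysis took over the HIV-uninfected set of Section 13.4 (247, 139 and 108), the variance factors below would be the same and the detectable differences larger.

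**1. Precision from the baseline value (linear model).** The variance factor is 1 − rho², and the equivalent sample-size factor is 1/(1 − rho²). Without adjustment, the difference detectable with 80% power is (2.241 + 0.842) × √(2/266) = 0.267 SD. With adjustment it is 0.267 × √(1 − rho²). Power at 0.267 SD is Φ(3.083/√(1 − rho²) − 2.241).

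| rho (assumed) | variance factor | equivalent n | detectable difference | power at 0.267 SD |
|---|---|---|---|---|
| 0 | 1.00 | 1.00 | 0.267 SD | 80% |
| 0.3 | 0.91 | 1.10 | 0.255 SD | 84% |
| 0.5 | 0.75 | 1.33 | 0.232 SD | 91% |
| 0.6 | 0.64 | 1.56 | 0.214 SD | 95% |

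These factors are exact only for linear models. For logistic and Poisson regression they are a rough guide.

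**2. What a three-arm F test would show.** The noncentrality is λ = n Σ(μᵢ − μ̄)². Let only the attention-matched control differ from the other two arms, by d = 0.267 SD. Then Σ(μᵢ − μ̄)² = 2d²/3 and λ = 266 × (2/3) × 0.267² ≈ 12.7. With 2 and 795 degrees of freedom, the F test at 0.05 rejects with 90% probability, although CHALO! 2.0 equals coupon only. If CHALO! 2.0 and attention-matched control both differ from coupon only by d, λ is the same. The test again rejects with 90% probability, although CHALO! 2.0 equals attention-matched control. A significant F therefore identifies neither stated contrast.

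**3. Does skewness matter?** Overdispersed counts were simulated for two arms of 266, with an assumed mean of 4, an assumed rate ratio of 0.75 for power, 1,500 runs per setting and skewness of 2.7 to 3.5. The nominal level is 2.5%, with a Monte Carlo standard error of √(0.025 × 0.975/1500) = 0.4 points.

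| Analysis | Power at correlation about 0.33 / 0.53 / 0.22 | Type I error across settings |
|---|---|---|
| Unadjusted two-arm comparison of means | 66% / 57% / 48% | 2.3–3.1% |
| Linear model with baseline | 72% / 73% / 50% | 2.5–3.1% |
| Robust Poisson, no baseline | 67% / 58% / 49% | 2.7–3.5% |
| Negative binomial with log baseline | 72% / 76% / 53% | 2.5–4.2% |

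The simple comparison stays close to its nominal level. Moving to a count model alone adds 1 to 2 points of power. Adding the baseline value to the linear model adds 2 to 16 points, so most of the gain comes from the baseline. The 4.2% for the negative binomial model is about four standard errors above nominal, since (4.2 − 2.5)/0.4 ≈ 4. Robust Poisson with baseline was not simulated.

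**The case against.** The strongest reply is that the plan, read as a whole, already provides most of this. Repeating the analyses above means two-sample comparisons plus a regression on Table 2 covariates, and Table 2 lists partners and condom use at month 0. Aim 2 follows the Aim 1 approach, and the Aim 1 regression adjusts for Table 2 covariates without condition. A two-group ANOVA is a t-test of exactly the contrast wanted. Section 12 also undertakes to "verify that distributions of measures meet" the assumptions of the planned tests, and the tests are to be used as appropriate.

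Much of this stands. A reader might infer that the plan commits to an ANOVA of follow-up values that ignores baseline, or to a single three-group F test. Neither is written, so baseline adjustment and the two contrasts are left open rather than ruled out. A reader might also infer that a skewed partner count makes the simple comparison invalid. The documents give no distribution for partners, and the simulation does not bear this out at about 266 per arm.

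What the reply does not settle is the guarantee. For Aim 2 the regression is qualified by "adjusting for covariates in Table 2 as required", and Section 12 acts only on observed differences. The partners row of Table 2 has five time points, and the plan does not say which serves as the covariate. Nothing requires the stratum. Section 12 names no fallback if a distribution fails its check.

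**Conclusion.** The point holds as a free improvement. For number of partners and consistent condom use, the plan does not fix the outcome's own baseline value or the randomisation stratum as covariates, and it does not fix CHALO! 2.0 against each control as the reported contrasts.

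The size is a 9% to 36% reduction in residual variance for an assumed correlation of 0.3 to 0.6. The correlation is not in the documents, and the formula is a linear-model approximation. The F-test result applies only if ANOVA is run across three arms, which the wording allows but does not state. The effect is confined to secondary outcomes: the primary analyses and their sample size are untouched.

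**What to change.** Complete the sentence in Section 13.3 and specify the main analysis of each outcome as a regression at a stated time point, in a stated set of participants:

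- **Number of partners:** Poisson regression with robust standard errors, in line with the Poisson methods already planned for testing frequency.
- **Consistent condom use:** logistic regression.
- **Both models:** include the month-0 value of that outcome and the randomisation stratum (prior HIV testing history, coded as used in the allocation) as fixed covariates, whether or not the arms differ at baseline.
- **Reporting:** give CHALO! 2.0 versus attention-matched control and CHALO! 2.0 versus coupon only as the two contrasts, each with an estimate and confidence interval. A three-arm test, if kept, should be supplementary.

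The cost is a few lines of SAP wording, best settled before outcome data are examined by arm. No new data and no change in sample size are needed.
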